The standard deviation of the difference in systolic BP is 16.7 mmHg and we can detect an 8.4 mmHg between-group difference using the above assumption. The assessment of endothelial function is another major goal of this application. Position papers on FMD studies 90 state the following: "Typically, significant improvement in FMD can be seen with 20 to 30 patients in a crossover design study and 40 to 60 patients in a parallel-group design study. In studies of this size, the minimal statistically significant improvement that can be detected with intervention is an absolute change in FMD of 1.5% to 2%." The SD of absolute change within subjects in our lab is 0.93%. The sample size proposed (160) will allow us to detect a change of as little as 0.45%. Notably, this change is much more sensitive—approximately one quarter of what is commonly seen with typical sample sizes in conventional FMD studies.

Analysis

The analyses will begin with descriptive statistics. Overall and by-group descriptive statistics will be calculated and examined graphically. Tests for differences in demographics between the early and delayed start groups and characteristics of dropouts will be computed using t-tests, chi square (or Fisher's exact tests if $n < 6$ per cell) to understand if potential differences exist, although such differences are not expected. Comparison of the three UACR strata will be done to assess if there are differences in the populations recruited. Randomization will be within UACR group so that these differences should not bias the trial.

Primary Analysis

To test the hypothesis that early start EPO will worsen the 24-hour DBP assessed by change from baseline to 12 weeks, a mixed model will be used to analyze the results.

We will fit two separate models:

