- model 1: The outcome variable will be 24h ambulatory diastolic BP. The predictors will be indicator variables for group (early or late start), time (baseline and 12 weeks), stratum (UACR: none, high, very high) and all interactions. The random component of the mixed model will include subject and time. Unstructured covariance will be used with estimation of marginal means by maximum likelihood. We expect the interaction between group by time to be significant. The random coefficient analysis does not require baseline systolic BP as a covariate. If the 3-way interaction term (group x time x stratum) is significant, then results will be reported within each stratum. Confirmatory analyses will utilize change from baseline in clinic diastolic BP.
- model 2: The outcome variable will be 24h ambulatory diastolic BP. The predictors will be indicator variables for period within the delayed start group (early or late), time (baseline and 12 weeks from start of period), stratum (UACR: none, high, very high) and

all their interactions. The random component of the mixed model will include subject and time. We expect the interaction between period by time to be significant. If the 3-way interaction term is significant, then results will be reported within each stratum.

Accounting for missing data

Ambulatory BP recording, the gold-standard to assess BP, is carried out only twice during the trial in the parallel group analysis, but clinic BP measurements occur every 4 weeks. Patients who drop out but have some post-baseline measurements of clinic BP will be included in the analyses, thus minimizing loss to follow up. We will impute ambulatory BP as follows: we will use the complete data to build a model that relates the follow-up mean 24-hour ambulatory diastolic BP from the baseline 24-hour ambulatory diastolic BP and the clinic measures using repeated measures Mixed Model regression - then use the expected value from the model for the missing value - and use PROC MI (which generates maybe 5 replicate values to insert variability into the imputation) so that there is a price to pay for imputing.

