Comparison of the cohort with these measurements will also be done to understand if the inferences based on the ambulatory BPs accurately reflect the differences between the treatment groups using the clinic BPs. Repeated measures mixed models (PROC MIXED in SAS) will be utilized to assess the overall differences between the treatment groups using the clinic BPs. Additional analyses will explore the nocturnal patterns between the groups in the ambulatory BPs as well as the pattern over time using circadian models of BP in each group.

Between-group changes in hypertension status from baseline to 12 weeks will be tested using logistic regression. Worsening of hypertension at any time point will be defined either as an increase in BP medication or an increase in seated clinic diastolic BP of ≥ 10 mmHg or systolic BP ≥ 20 mmHg. The McNemar test will be used to compare within-group change in hypertension status from 12w to 24 w to that in the control period of 0 to 12w.

To test the hypothesis that EPO is causal to EIH via worsening of FMD, we will evaluate changes from baseline in FMD. That is, we will test if the worsening is a mediation effect using the technique described by Judd and Kenny⁹⁶ and elaborated by MacKinnon⁹⁷. The technique, expanded here for more than one potential mediator employs three regression equations:

- A. $Y = \beta_0 + \tau X_p + \varepsilon$
- B. $X_i = \beta_0 + \alpha_i X_p + \varepsilon$
- C. $Y = \beta_0 + \tau' X_p + \beta_1 X_1 + \dots + \beta_i X_i + \dots + \beta_k X_k + \varepsilon$ for all mediators together,
or $Y = \beta_0 + \tau' X_p + \beta_i X_i \varepsilon$ for each mediator separately

Y is the outcome result (e.g., change in 24-hour diastolic systolic BP), X_p is the group (early vs delayed start) and X_i represent the k purported mediators. The total effect of the treatment on the outcome (measured by the coefficient, τ) is the sum of direct effect (τ') of the treatment and the mediated, or indirect, effects ($\alpha_i \beta_i$). Mediation is established when four conclusions are met: (1) the treatment predicts the outcome variable (supported by a test of statistical significance of τ in equation [A]); (2) the treatment causes the potential mediator (α_i is significant in [B]); (3) the mediator causes the

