outcome variable controlling for the group assignment (β_i is significant in [C] and $\tau' < \tau$, which provides evidence for mediation rather than suppression); and (4) the mediated effect is statistically significant. For mediators that satisfy conclusions 1 through 3, the significance of mediation (conclusion 4) will be determined via interval estimation of the mediated effect using the asymptotic variance derivation of Sobel ⁹⁸ since the outcomes are the continuous measures. Additional analyses that look at thresholds of change (binary: worsening of hypertension or not) will utilize bootstrapping methods and logistic regression. The proportion of the effect mediated is calculated as the ratio of the indirect effect to the total effect, or $\alpha\beta/\tau$.

The primary outcome for flow-mediated dilatation is change in FMD from baseline to 4 w in those treated with EPO compared to time controls. Predictors of this change will be baseline values of the following biomarkers: plasma ADMA, urine nitrate and nitrite, and plasma renin, aldosterone, and endothelin-1 and change from baseline to 4 w in the above biomarkers. In addition, the baseline FMD will be an independent variable. This analysis will use regression models similar to the above-listed analyses.

Pre-specified sub-group analyses for BP response

- Effect of age: The effect of age (e.g., 65 or more and <65) will be tested using interaction effects.
- Effect of volume overload: Volume overloaded subjects are more likely to show worsening EIH with EPO therapy. In people with volume overload, renin and aldosterone levels are expected to be low and 24-hour urine Na high. We will dichotomize the baseline levels of these markers and examine the outcome on ambulatory BP using interaction effects.

Safety analysis

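### Mediation equations A to C leave out baseline 24-hour DBP, baseline FMD and the UACR stratum, giving up modest precision that already collected data could recover

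*Combined protocol and SAP*

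**What the plan says.** The mediation regressions are in Statistical Methods, Analysis, after the missing-data text. Equations A and B have an intercept and the group indicator. Equation C adds the mediators, together or one at a time: "X_p is the group (early vs delayed start) and X_i represent the k purported mediators". Both sides are change scores. The outcome is given as "Y is the outcome result (e.g., change in 24-hour diastolic systolic BP", read here as diastolic, and for the mediator the plan says "we will evaluate changes from baseline in FMD". No sentence adds a covariate to A, B or C.

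Elsewhere the plan does use these variables:

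- Analysis, opening paragraph: "Randomization will be within UACR group so that these differences should not bias the trial".
- Primary Analysis, model 1: the predictors include "stratum (UACR: none, high, very high) and all interactions".
- The separate regression of FMD change on biomarkers: "In addition, the baseline FMD will be an independent variable".

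The one reason given for omitting a baseline is "The random coefficient analysis does not require baseline systolic BP as a covariate". It belongs to the primary mixed model and names systolic pressure, so it does not cover A to C.

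**The concern.** A change score is correlated with its own baseline through regression to the mean. Leaving the baseline out of a change-score regression therefore leaves removable variance in the residual. Ambulatory BP and FMD are measured at baseline, and UACR defines the randomisation strata, so adjustment needs no new data.

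Precision matters here because the plan accepts mediation only if tau, alpha, beta and the product alpha × beta are all significant. Missing one of them ends the claim. Equation A also estimates the total effect without the stratum term that primary model 1 contains. The tau used in the first mediation condition, and as denominator of the proportion mediated, thus comes from a different model than the main result.

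**Working it through.** **The plan's own figures.** Sample Size gives an SD of 10.3 mmHg for the change in 24-hour DBP, a difference of 5 mmHg, two-tailed tests and 80% power. Alpha is not stated; 0.05 is assumed. The normal approximation gives 2 × (1.960 + 0.842)² × 10.3² / 5² = 66.6, so 67 per group. The noncentral t gives 68 (power 80.2%), and 68 / 0.85 = 80 per group. The stated 68, 80 and 160 reproduce. No sample size is stated for the mediation analysis.

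**Formula.** With equal variance at both visits and correlation ρ, a change score has variance 2σ²(1 − ρ). A baseline-adjusted analysis has residual variance σ²(1 − ρ²). The ratio is (1 + ρ)/2.

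**Equation A, adding baseline DBP.** The documents give no cross-sectional SD, so it is assumed, and ρ = 1 − 10.3² / (2 × SD²).

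| Assumed SD (mmHg) | ρ | Variance ratio | Reduction |
|---|---|---|---|
| 10 | 0.470 | 0.735 | 27% |
| 11 | 0.562 | 0.781 | 22% |
| 12 | 0.632 | 0.816 | 18% |
| 13 | 0.686 | 0.843 | 16% |

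A wider range of 8 to 14 mmHg gives ratios of 0.59 to 0.87. The 10.3 was measured over 4 weeks and is applied here to 12.

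**Equation B, adding baseline FMD.** The section on measurement of endothelial dysfunction reports 0.93% within and 1.77% between subjects, in healthy volunteers.

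- If these are per-measurement components: ρ = 1.77² / (1.77² + 0.93²) = 0.784, ratio 0.892, an 11% reduction. If 1.77% is the total SD, ρ = 1 − 0.93² / 1.77² = 0.724, ratio 0.862, a 14% reduction.
- If 0.93% is the SD of change, as Sample Size says, the per-visit variance is 0.93² / 2 = 0.432. Then ρ = 3.133 / 3.565 = 0.879, ratio 0.939, about a 6% reduction.

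**Stratum.** It costs 2 degrees of freedom out of about 134. No between-stratum variance is given, so its gain cannot be computed.

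**Path coefficients by simulation.** Settings: 68 per arm, 6,000 runs, assumed DBP SD 12, FMD SDs 0.93 and 1.77, true alpha −0.9, beta −2, direct effect 2 mmHg, hence a true indirect effect of 1.8. Patients have stable levels plus independent visit error, and the two baselines are uncorrelated. The entries are standard errors.

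| Covariates added | tau | alpha | beta | alpha × beta |
|---|---|---|---|---|
| None (the plan) | 1.807 | 0.225 | 0.683 | 0.791 |
| Baseline DBP in A and C | 1.653 | 0.225 | 0.623 | 0.743 |
| Baseline FMD in A, B and C | 1.809 | 0.212 | 0.728 | 0.804 |
| Both in A, B and C | 1.654 | 0.213 | 0.663 | 0.754 |

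Adding both everywhere lowers the standard error of the indirect effect by (0.791 − 0.754) / 0.791 = 5%. Baseline DBP in A and C with baseline FMD in B only lowers it by about 7%. Across repeats the range is about 5% to 8%.

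**Bias in beta when the baselines correlate at −0.3 (true beta −2).**

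- Stable levels plus visit error: the plan's equation gives −1.99, baseline DBP alone −2.00, both baselines −2.28. With both, the indirect effect is 2.04 against 1.80, about 14% too large.
- Each change depends on its own baseline: the plan's equation gives −2.33, and its indirect effect is about 16% too large. Both baselines give −2.00, and baseline DBP alone is also unbiased.

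**The case against.** The strongest objection concerns equation C. Baseline FMD added there alone raises the standard error of beta from 0.683 to 0.728. With both baselines in C, beta can be biased when patients differ in stable, correlated levels, because change scores cancel such differences and conditioning on noisy baselines brings them back. This stands. A reader might infer that adding every baseline to every equation costs nothing, or that doing so controls the confounding of a non-randomised mediator. The documents support neither, since they give no basis for choosing between the two data models above.

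A reader might also turn the variance reduction in A into 19% to 36% more patients (1/0.843 and 1/0.735) and apply it to the trial. That does not follow. Equation A is not the test of the BP effect; mixed model 1 is, and it already includes stratum.

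Nor does leaving baseline FMD out of B contradict its use in the biomarker regression. The two analyses ask different questions. It shows only that the plan already regards baseline FMD as a usable covariate.

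It is also fair that A to C are presented as the general form of a cited method, and that the SDs are assumed or come from healthy volunteers. But no text in the plan adds a covariate, and the direction of the gain in A and B does not depend on the exact SD.

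**Conclusion.** The omission is in the text, and a limited adjustment improves the analysis. With baseline DBP in A and C and the mediator's baseline in B, precision improves for tau, alpha, beta and the indirect effect, and neither data model examined shows bias.

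The gain is moderate for tau, at 16% to 27% of variance, and rests on the assumed DBP SD of 10 to 13 mmHg. It is small for alpha: 11% if the volunteer SDs carry over to anaemic CKD patients, and nearer 6% if 0.93% is the SD of change. It is small for the indirect effect, at 5% to 8% of the standard error. No figure can be given for stratum.

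The unadjusted estimates of tau and alpha are not biased by the omission, because group is randomised. Whether the plan's beta is biased depends on the data model and cannot be settled from the documents. This is a secondary mechanistic analysis, and the primary DBP test is untouched.

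**What to change.** Amend the mediation text before analysis:

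1. Equations A and C: add baseline 24-hour DBP and UACR stratum.
2. Equation B: add the mediator's own baseline and UACR stratum.
3. Report C with the mediator baselines added as a sensitivity analysis only, and say that this may remove or add bias in beta.
4. State that tau = tau′ + alpha × beta is exact only when the equations share covariates, so under items 1 and 2 the decomposition and the proportion mediated are approximate.
5. Correct the outcome wording, which names both diastolic and systolic pressure.

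All covariates are already collected. The cost is SAP wording and 3 degrees of freedom per equation (2 for stratum, 1 for the baseline). The sensitivity version of C uses one more for each mediator entered.

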Using an uSmart NexGen Ultrasound 3300 (Terason, Burlington, MA) equipped with two-dimensional imaging, color and spectral Doppler, an internal electrocardiogram (EKG) monitor and a

[figure not shown]

Figure 3: Example of flow-mediated dilatation in a healthy volunteer from 24 Aug 2017

duplicate. The change in post-stimulus diameter at peak dilation as a percentage of the baseline diameter will be reported as endothelial function.

Analysis will be automated using a validated software (Vascular Analysis Tools 6, MIA-LLC, Coralville, IA). We have reported a clinical trial using FMD from our laboratory ¹⁸. **Figure 3** shows the results of FMD from our laboratory in a normal healthy volunteer using the above software. Although FMD requires an ultrasound machine, high frequency transducers, and a trained technician capable of measuring the diameter of the brachial artery before and after ischemia in a reproducible manner, we use the FMD technique because it is the reference standard for endothelial function ^{94,95}. We have previously reported FMD to be 12.9% in normal healthy volunteers with within-subject standard

high frequency vascular transducer (16 to 5 mHz, 16L5 probe), ultrasonography will be performed by a trained technician using a standardized protocol ^{91,92}.

Participants will be positioned supine with the arm placed in a comfortable position to image the brachial artery in a longitudinal plane. A segment of brachial artery 5-10 cm above the elbow with clear anterior and posterior intimal interfaces between the lumen and the vessel wall will be selected. A sphygmomanometric cuff placed on the forearm will be rapidly inflated to suprasystolic pressure (250 mmHg) for 5 minutes to produce ischemia using an air source coupled to a rapid cuff inflator (Hokanson E 20 Rapid Cuff Inflator; E.C. Hokanson, Inc).

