Longitudinal resting images will be acquired before inflation. Blood flow estimated by the pulsed Doppler velocity signal using the outer envelope technique to calculate the velocity time integral will be obtained from a mid-artery sample volume at baseline and upon immediate cuff release to assess hyperemic velocity. Peak hyperemic velocity will be determined from the first complete velocity envelope after cuff release. Higher values of hyperemic velocity represent better microvascular dilatation ⁹³. Longitudinal images of the artery in B mode will be continuously recorded for 3 min after cuff deflation. Images will be recorded digitally using an R-wave gated digitizing interface external to the machine (MIA- LLC, Coralville, IA).

A few minutes after deflation, another image will be acquired to reflect a reestablished baseline. The above procedure is repeated to acquire the images in

deviation of 0.93% and between-subject standard deviation of 1.77%. Thus, the test-retest coefficient of variation was 7.2% in our laboratory.

Biomarker measurements

We may use specimen collected as part of this study for analysis of DNA which may include whole genome sequencing. Plasma endothelin-1 will be measured using validated ELISA kits (R&D systems, Inc., Minneapolis, MN). 24h urinary nitrite and nitrate and total nitrates will be measured using the Greiss reaction using kits from R&D systems, Inc. Renin and aldosterone will be measured using a commercial laboratory (LabCorp, Burlington, NC). Plasma ADMA will be measured using LCMS in our biochemistry core lab. The usual labs such as blood counts, chemistries, urine albumin and Na will be measured in the hospital laboratory. Renin + aldosterone lab testing will require the participants to be resting in seated position for at least 15 minutes prior to blood draw.

STATISTICAL METHODS

Outcome Variables

The outcome variables are as follows:

1. Change from baseline to 12 weeks in diastolic BP in EPO treated patients compared to delayed start controls. In the waitlisted group, we will measure the change from 12 weeks to 24 weeks compared to the change from 0 to 12 weeks.

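### The FMD mediation model treats observed FMD change as error-free, so in its single-mediator form the mediated share is attenuated by an amount the documents do not fix; the plan needs a reliability estimate and a sensitivity analysis.

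*Combined protocol and SAP*

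**What the plan says.** The Analysis section states the mechanistic aim: "To test the hypothesis that EPO is causal to EIH via worsening of FMD, we will evaluate changes from baseline in FMD". It gives three regressions: A (outcome on group, coefficient τ), B (mediator on group, α) and C (outcome on group and mediator, τ' and β). In these, X_p "is the group (early vs delayed start) and X_i represent the k purported mediators". Equation C is specified both for all mediators together and for each one separately. Mediation requires, among other conditions, a significant β with τ' < τ. The indirect effect is tested with the Sobel variance, and the share is reported as αβ/τ. No measurement-error term, reliability estimate or sensitivity analysis for the mediator is stated.

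The documents describe the variability of FMD in two ways:

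- **Measurement of endothelial dysfunction:** "We have previously reported FMD to be 12.9% in normal healthy volunteers with within-subject standard" "deviation of 0.93% and between-subject standard deviation of 1.77"%. It adds: "Thus, the test-retest coefficient of variation was 7.2% in our laboratory".
- **Sample Size:** "The SD of absolute change within subjects in our lab is 0.93"%, followed by "The sample size proposed (160) will allow us to detect a change of as little as 0.45"%.

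FMD is acquired twice at each session ("The above procedure is repeated to acquire the images in" duplicate), but no rule for combining the two values is given. By the Figure 2 schedule, both arms have FMD at baseline and week 4. The delayed-start arm also has it at week 12, when its EPO is due to begin.

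**The concern.** Random error in FMD does not bias α, because α is a difference between arm means. It does affect β, because β is estimated from variation in FMD change among patients in the same arm, and part of that variation is noise. In the simple case the FMD-to-BP slope is flattened, and the portion of the effect it should carry is credited to τ'.

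The trial asks whether EPO raises BP through endothelial dysfunction. A true FMD pathway could be reported as mostly direct effect, and the requirement that β be significant becomes harder to meet. Following the plan exactly would not remove this.

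**Working it through.** **Inputs from the documents.** FMD SD 0.93%; mean FMD 12.9% in healthy volunteers; test-retest CV 7.2%; detectable FMD difference 0.45%; 68 completers per arm; 80% power, two-tailed; SD of change in 24-hour diastolic BP 10.3 mmHg; target difference 5 mmHg. **Assumed:** two-sided α level 0.05 (no number is given), and s, the within-arm SD of true FMD change.

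**1. Reproduce the plan's figure.** Detectable difference = (1.960 + 0.842) × 0.93 × √(2/68) = 0.447%, or 0.450% with the t distribution. The stated 0.45% reproduces if 0.93% is the SD of a change.

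**2. Check what 0.93% is.** 0.93/12.9 = 7.2%, so the stated CV fits the SD of an FMD level. The SD of the error in a change would then be 0.93 × √2 = 1.32%. The detectable difference would be 0.63%, and power for 0.45% with 68 per arm about 51%. If instead 0.93% is a single-scan SD of change and duplicates with independent errors are averaged, the figure is 0.93/√2 = 0.66%. If it is a single-scan SD of a level and duplicates are averaged, it returns to 0.93%.

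**3. Attenuation.** With one mediator, classical error of SD e in the change, and no shared causes of FMD and BP, the expected estimate of β is λβ, where λ = s²/(s² + e²).

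| Assumed s | e = 0.66% | e = 0.93% | e = 1.32% |
|---|---|---|---|
| 0.45% | 0.2025/0.6350 = 0.32 | 0.2025/1.0674 = 0.19 | 0.2025/1.9323 = 0.10 |
| 0.93% | 0.8649/1.2974 = 0.67 | 0.8649/1.7298 = 0.50 | 0.8649/2.5947 = 0.33 |
| 1.5% | 2.25/2.6825 = 0.84 | 2.25/3.1149 = 0.72 | 2.25/3.9798 = 0.57 |

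The low end of s, 0.45%, is an assumption. It only happens to equal the detectable group difference.

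**4. Simulation of A to C** (68 per arm, τ = 5 mmHg, SD of BP change 10.3 mmHg, true mediated share 50%). With e = 0.93%, the share was estimated at about 11%, 25% and 39% for s of 0.5%, 0.93% and 1.77%, which matches 50% × λ with λ = 0.22, 0.50 and 0.78. τ' rose from 2.5 to about 4.4, 3.8 and 3.0 mmHg. α and τ stayed unbiased. Shrinkage was the same for group effects on FMD of 0.45%, 0.9% and 1.8%.

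**5. Power for a significant β** (same set-up, e = 0.93%). It fell from about 81% to 22% with s and the group effect both 0.45%, and from about 81% to 67% with both 1.5%. With s = 0.93% and a group effect of 0.45% it was still 99%, yet the reported share was halved.

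**6. Beyond the simple case.** Two mediators were entered together, with error also in a biomarker correlated with FMD. A true FMD slope of 0 was then estimated as −0.55, and in a second example a slope of −1 as −2.15. With one mediator and a correlated cause omitted, slopes of 0 and −1 became −1.10 and −2.77. These bias the FMD slope away from zero.

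**The case against.** A reader might infer that the bias is severe because the noise (0.93%) is about twice the effect sought (0.93/0.45 = 2.07). The documents do not support that. The group effect does not enter λ, as step 4 shows; what matters is noise variance against the variance of true individual changes within arm, which is nowhere stated. For the same reason no single percentage understatement can be claimed. The 0.93% also comes from healthy volunteers, not from CKD patients.

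A reader might also infer that the direction is known, so that the uncorrected share is a lower bound. That holds only under the assumptions in step 3. The plan also specifies the joint form of equation C. Group is randomized but FMD change is not, and the equations contain no covariates, so causes common to FMD and BP are uncontrolled.

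The remedy has limits too. If the control arm's variance of change is taken as the error variance, and true changes vary equally in both arms, the expected true variance left is zero and the estimate is negative about half the time. If only treated patients vary truly, with s = 0.45% and e = 0.93%, it is still negative about 20% of the time (F with 67 and 67 df).

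Finally, the primary diastolic BP comparison is untouched, and duplicate FMD is already planned. All of this stands. None of it answers the omission in the single-mediator equation, which the plan does specify.

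**Conclusion.** The point holds in limited form. Equation C takes a noisy FMD change as exact. In the single-mediator form, with classical error and no mediator-outcome confounding, β and αβ/τ are attenuated by λ and the remainder moves to τ'. For assumed s of 0.45% to 1.5%, λ lies between about 0.10 and 0.84 across the three readings of 0.93%. Neither s nor the correct reading can be settled from the documents, which is the reason to estimate reliability within the trial. Outside those assumptions the direction is not determined. The point concerns the mechanistic conclusion only, and the remedy is a low-cost improvement to the analysis plan.

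**What to change.** In the analysis plan:

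1. State that the FMD value at each visit is the mean of the duplicate acquisitions.
2. Estimate the reliability of FMD change from the duplicates and from the delayed-start arm's untreated measurements (baseline, week 4, week 12), leaving out values taken after any early start of EPO. Duplicates capture only error within a visit, so they give a floor for the error variance. The variance of untreated change also contains true change, so it gives a ceiling.
3. Pre-specify, beside the planned estimate, a sensitivity analysis of the single-mediator indirect effect over a stated range of error variances, by regression calibration or a latent-variable model. Limit the range to values that leave positive true variance.
4. Reconcile the two descriptions of 0.93%, and recompute the detectable FMD difference if it is the SD of a level.
5. Do not describe the uncorrected share as a lower bound, except explicitly under the single-mediator, classical-error, no-confounding assumptions.

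The cost is some wording and one added analysis, with no new visits or measurements. The downside is a wider and possibly unstable interval for the corrected estimate.

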In isolated perfused rodent kidneys, EPO treatment results in RAAS-stimulated sodium retention ⁷⁸. This is in sharp contrast to normal human volunteers, wherein EPO treatment caused reduction in plasma volume, plasma renin activity and aldosterone ⁷⁹. However, in rats with subtotal nephrectomy treated with EPO, in terms of treatment there is no unique effect on BP lowering of RAAS blockade. This is because the reduction in systolic BP was similar when rats were treated with traditional triple therapy (reserpine, hydralazine, hydrochlorothiazide) or with the RAAS blockers captopril or losartan ⁴⁷. In CKD patients treated with EPO, the evaluation of RAAS remains incomplete.

Blood viscosity

Blood viscosity rises in parallel with blood Hgb and has been cited as a mechanism of EIH. However, not all patients who have correction of anemia get hypertensive. Thus, the change in blood viscosity by itself appears to be insufficient to account for EIH.

Hypoxia Inducible Factors (HIF) Prolyl Hydroxylase Inhibitors

HIF stabilizers stimulate not only erythropoiesis but also many other genes responsible for angiogenesis, tumor growth, cell proliferation, and metabolism ⁸⁰. HIF stabilizers are in Phase III clinical trials for the treatment of anemia in CKD. It remains unclear whether HIF stabilizers will protect or predispose people with CKD to hypertension. HIF stabilizers may aggravate hypertension by several mechanisms. For example, chronic intermittent hypoxia through HIF signaling in the carotid body is thought to provoke systemic hypertension ⁸⁰. A 2016 study showed in both in vitro and in vivo rodent models that hypoxia provoked inorganic phosphorus-induced vascular smooth muscle calcification. In this rodent model, roxadustat, an oral HIF stabilizer, in fact enhanced vascular calcification. Vascular calcification is common in CKD and contributes to arterial stiffness. Increased arterial stiffness is strongly associated with elevated interdialytic ambulatory BP ⁸¹. The downstream effect of long-term use of HIF stabilizers may therefore be hypertension.

[figure not shown]

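### When several mediators are fitted together, the check τ' < τ is one shared result and cannot tell mediation from suppression for any single mediator

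*Combined protocol and SAP*

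**What the plan says.** The mediation paragraphs come in STATISTICAL METHODS, Analysis, after the text on missing data. They set out to test whether EPO raises BP by worsening FMD, then widen the method: "The technique, expanded here for more than one potential mediator employs three regression equations". Equation A regresses the outcome on group (coefficient τ). Equation B regresses each mediator on group (α_i). Equation C regresses the outcome on group and mediators (τ' and β_i), either "for all mediators together" or "for each mediator separately". The plan does not say which form decides. It also states that the total effect "is the sum of direct effect (τ') of the treatment and the mediated, or indirect, effects".

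Mediation is declared when four conclusions hold:
1. τ is significant.
2. α_i is significant.
3. β_i is significant in C and τ' < τ, "which provides evidence for mediation rather than suppression".
4. "4) the mediated effect is statistically significant", judged by a Sobel interval.

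The proportion mediated is then αβ/τ. FMD is the only mediator of BP named; the k mediators are not listed.

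**The concern.** Conclusion 3 is meant to protect each mediator's label against suppression, that is, against an indirect effect running opposite to the total effect. In the joint form of C there is one τ and one τ', so the comparison carries no mediator index. It is attached to a test of β_i that does carry one.

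No other conclusion supplies the missing sign. Conclusions 1, 2 and 4 and the β_i part of conclusion 3 are all tests of significance, and a significantly negative α_iβ_i satisfies them as well as a positive one. A pathway through which EPO lowers BP could therefore be declared a mediator of the BP rise. Equally, FMD could be refused that status because of another variable in the model. The second error would give a wrong answer to the trial's main mechanistic question.

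**Working it through.** **Inputs from the plan (Sample Size).** Between-group difference 5 mmHg, SD of change 10.3 mmHg, two-tailed, 80% power, 85% completing. The significance level is not stated; 0.05 is assumed.

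**The plan's own figure.** n per arm = 2 × (1.960 + 0.842)² × 10.3² / 5² = 66.6 by the normal formula and 67.6 by the t-test, so 68. Then 68/0.85 = 80 per arm and 160 in total. The stated figures reproduce. In SD units τ = 5/10.3 = 0.485.

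**The identity.** With least squares on the same patients:
- one mediator in C: τ − τ' = α_iβ_i, so τ' < τ is exactly the statement α_iβ_i > 0;
- k mediators in C: τ − τ' = α_1β_1 + … + α_kβ_k, so τ' < τ says only that the sum is positive.

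This is the plan's own decomposition rearranged. In simulated trials it held to within 2 × 10⁻¹⁴.

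**Hand example, in mmHg with τ = 5.**
- Scenario A: indirect effects +4.8 and −2.8. The sum is +2.0 and τ' = 3.0 < 5, so both pass, including the suppressor. Its proportion mediated is −2.8/5 = −56%.
- Scenario B: indirect effects +2.8 and −4.8. The sum is −2.0 and τ' = 7.0 > 5, so both fail, including the true mediator.

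**Simulation of the four conclusions.** 4,000 trials per scenario, 68 per arm. Mediator effects are assumed: α = 0.8 for each, residual SD 1, residuals uncorrelated.

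| Joint form of C | Scenario A | Scenario B | Both +2.8 |
|---|---|---|---|
| τ' < τ holds | 92.1% | 7.6% | 100% |
| Suppressor labelled a mediator, plan rule | 76.2% | 7.2% | none present |
| True mediator accepted, plan rule | 76.7% | 7.5% | about 79% |
| True mediator accepted, own-sign rule | 79.9% | 80.3% | about 79% |
| Suppressor accepted, own-sign rule | 0.0% | 0.0% | none present |

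In Scenario B, 72.8% of trials reject the true mediator on the shared check alone.

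**Dependence on assumed effects** (68 per arm, 3,000 trials, SD units, uncorrelated residuals).
- Strong suppressor, outweighed by FMD (FMD α −0.48 to −0.8, β −0.4 to −0.5; suppressor α −0.5 to −0.8, β 0.25 to 0.35): suppressor labelled a mediator in 43–69%.
- Suppressor outweighing FMD (suppressor α −0.8, β 0.5; FMD α −0.6 to −0.7, β −0.3 to −0.35): FMD accepted in 4–10%, against 72–78% under the own-sign rule.
- Weak to moderate suppressor (FMD α −0.5, β −0.35; suppressor β 0.2): labelled a mediator in 3%, 6% and 10% for suppressor α of −0.2, −0.3 and −0.4. A further rerun with a moderate suppressor gave 5–11%. FMD acceptance was 58–62%, against 61–62% under the own-sign rule, so almost nothing is lost.

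**Is the separate form a safe fallback?** With uncorrelated mediators, yes: the suppressor is accepted in 0.0% of trials in A and B, and the true mediator in 79.9% (A) and 78.0% (B). With residual correlation 0.5, no: in Scenario B the separate form accepts the true mediator in 4.5%, against 76.2% for the joint form with an own-sign rule. The omitted mediator biases β_i when the two are correlated.

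**The case against.** The strongest reply is about scope. The hypothesis sentence names FMD alone, and with one mediator the check is exact. The biomarkers (ADMA, nitrate and nitrite, renin, aldosterone, endothelin-1) are listed in Outcome Variables as predictors of FMD change, not as parallel mediators of BP. This stands as a limit. It does not remove the point, because the plan expressly extends the method to several mediators and writes out the joint model.

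A second reply is that the planned output would expose a suppressor: its interval would lie wholly below zero and its proportion mediated would be negative. That is true and reduces the harm. But neither sign is a criterion, and a reader applying the four conclusions as written would still declare mediation. Nor does it stop the shared check from rejecting a true mediator.

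A third reply is that the large error rates need large effects. That also stands. A suppressor with α −0.8 and β 0.5 lowers diastolic BP by 0.8 × 0.5 × 10.3 = 4.1 mmHg, close to the whole 5 mmHg design effect.

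A reader might infer that suppression through renin and aldosterone is to be expected, because the Background describes a study "wherein EPO treatment caused reduction in plasma volume, plasma renin activity and aldosterone". The documents do not support that. Those subjects were healthy volunteers, and the same section contrasts them with rodent kidneys in which EPO led to sodium retention through this system. It reports raised renin mRNA in rat kidney and greater angiotensin II sensitivity in hemodialysis patients, and calls the evidence in EPO-treated CKD patients incomplete. The subgroup section links low baseline renin and aldosterone with worse, not milder, EPO-induced hypertension. The sign of any such indirect effect is open.

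**Conclusion.** The rule is wrong as written for the joint form of C with two or more mediators: the check is one shared result and cannot do, mediator by mediator, what conclusion 3 says it does. This follows from the plan's own decomposition and does not depend on sample size. A wrong label needs indirect effects of opposite sign.

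The frequency is illustrative only. At 68 per arm, τ = 5/10.3 SD and an assumed level of 0.05, a suppressor is labelled a mediator in about 5–11% of trials if moderate and about 40–75% if strong. A suppressor stronger than FMD cuts FMD acceptance to about 4–10%, from about 72–80% under an own-sign rule. The documents give no mediator effects from which to choose among these.

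Two stronger readings are not supported: that the test of FMD as sole mediator is invalid, and that mislabelling is likely in this trial. The point concerns the mechanistic mediation analysis; the primary diastolic BP comparison is untouched.

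**What to change.** In the mediation paragraphs:
- State that the joint form of C decides whenever more than one mediator is analysed, and list the mediators.
- For that form, replace τ' < τ in conclusion 3 with the requirement that α_iβ_i has the same sign as τ.
- In conclusion 4, require the interval for α_iβ_i to exclude zero in that direction.
- Report an interval wholly on the opposite side as suppression, without a proportion mediated.
- Use τ' < τ only when a single mediator is analysed, where it is equivalent to the sign rule.

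The cost is a few sentences of wording. No new data or extra model fits are needed, and the change is best made before results are known.
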